5. PARTICIPANT ENTRY

INCLUSION CRITERIA

Study 1:

- Healthy volunteers (body mass index (BMI) of 18-35 kg/m²)
- Age between 18-65 years (inclusive)

Study 2:

- Healthy volunteers (body mass index (BMI) of 18-35 kg/m²)
- Age between 18-65 years (inclusive)

Study 3:

- Healthy volunteers (body mass index (BMI) of 18-35 kg/m²)
- Age between 18-65 years (inclusive)

EXCLUSION CRITERIA

Study 1, 2, 3:

- Weight change of ≥ 3 kg in the preceding 2 months
- Current smokers

- Substance abuse
- Excess alcohol intake
- Pregnancy
- Diabetes
- Cardiovascular disease
- Cancer
- Gastrointestinal disease e.g. inflammatory bowel disease or irritable bowel syndrome
- Kidney disease
- Liver disease
- Pancreatitis
- Started new medication within the last 3 months likely to interfere with energy metabolism, appetite regulation and hormonal balance, including: anti-inflammatory drugs or steroids, antibiotics, androgens, phenytoin, erythromycin or thyroid hormones.
- Involved in current research or have recently been involved in any research prior to recruitment in the past 12 weeks.

WITHDRAWAL CRITERIA

The safety of the study participants takes priority. Any significant adverse event (as assessed by the researchers) will halt the study and the ethics committee and sponsor will be informed as per standard protocol. All adverse events will be recorded and investigators will review each adverse event as it arises. In addition, participants will be free to withdraw at any time and are not required to give a reason.

5. ADVERSE EVENTS

Adverse Event (AE): Any untoward medical occurrence in a patient or clinical study subject.

Serious Adverse Event (SAE): Any untoward and unexpected medical occurrence that:

- results in death
- is life-threatening – refers to an event in which the subject was at risk of death at the time of the event; it does not refer to an event which hypothetically might have caused death if it was more severe.
- requires hospitalisation, or prolongation of existing inpatients' hospitalisation.
- results in persistent or significant disability or incapacity
- is a congenital abnormality or birth defect

Medical judgement should be exercised in deciding whether an AE is serious in other situations. Important AEs that are not immediately life threatening or do not result in death or hospitalisation

but may jeopardise the subject or may require intervention to prevent one of the other outcomes listed in the definition above, should also be considered serious.

REPORTING PROCEDURES

All adverse events should be reported. Depending on the nature of the event the reporting procedures below should be followed. Any questions concerning adverse event reporting should be directed to the Chief Investigator in the first instance.

Non-serious AEs

All such events, whether expected or not, should be recorded.

Serious AEs (SEAs)

An SAE form should be completed and faxed to the Chief Investigator within 24 h. However, relapse, death and hospitalisations for elective treatment of a pre-existing condition do not need reporting as SAEs.

All SAEs should be reported to the xxxx Research Ethics Committee where in the opinion of the Chief Investigator the event was:

- ‘related’, i.e. resulted from the administration of any of the research procedures; and
- ‘unexpected’, i.e. an event that is not listed in the protocol as an expected occurrence.

Reports of related and unexpected SAEs should be submitted within 15 days of the Chief Investigator becoming aware of the event, using the NRES SAE form.

Local investigators should report any SAEs to the sponsor and their Local Research Ethics Committee and/ or Research and Development Office.

Contact details for reporting SAEs
[contact], attention [name]
Please send SAE forms to [name]
[contact] (Mon to Fri 09.00- 17.00)

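### The protocol makes death the first criterion for a serious adverse event, then exempts death from SAE reporting without any condition on cause

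*Combined protocol and SAP*

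**What the plan says.** All the conflicting text is in the section headed Adverse Events.

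- **Definition.** An SAE is "Any untoward and unexpected medical occurrence that" meets one of five listed criteria. The first is "results in death". Another is "requires hospitalisation, or prolongation of existing inpatients' hospitalisation".
- **Form to the Chief Investigator.** "An SAE form should be completed and faxed to the Chief Investigator within 24 h".
- **Exemption.** The next sentence reads: "However, relapse, death and hospitalisations for elective treatment of a pre-existing condition do not need reporting as SAEs".
- **Ethics report.** "All SAEs should be reported to the xxxx Research Ethics Committee where in the opinion of the Chief Investigator the event was" both related and unexpected. The time limit is: "Reports of related and unexpected SAEs should be submitted within 15 days of the Chief Investigator becoming aware of the event".
- **Local report.** "Local investigators should report any SAEs to the sponsor and their Local Research Ethics Committee and/ or Research and Development Office".

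Two general provisions sit outside this route. The Reporting Procedures open by requiring that every adverse event be reported, by whichever of the procedures below suits its nature. The Withdrawal Criteria under Participant Entry say that all adverse events are recorded and reviewed. They add that an event the researchers judge significant halts the study and is notified to the ethics committee and sponsor under a standard procedure that is not supplied.

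**The concern.** The same event is placed inside the SAE definition and then taken out of SAE reporting. An exemption for planned admissions is self-explanatory and carries its own qualifier. The exemption for death carries none: it does not depend on cause, on relatedness to the study procedures, or on whether the death was expected.

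Nor does the population supply a reason. Participants are healthy volunteers, with cancer and cardiovascular, kidney and liver disease excluded, so there is no index disease to relapse or from which death might be anticipated.

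What is at stake is whether the defined, time-limited route applies to the gravest event the trial could produce. Taken literally, the section names a 24-hour form for a life-threatening event that the participant survives and exempts the fatal one. Staff would have to choose between contradictory sentences at the moment they most need a clear rule.

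**Working it through.** The protocol gives no figure to reproduce on this point. The check compares the sentences and counts the steps affected.

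**1. Does the elective-treatment qualifier limit the exemption for death?** No. It fits hospitalisations; a death for elective treatment makes no sense.

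**2. Is the exemption confined to expected deaths?** The sentence does not say so. The section treats an event as unexpected when the protocol does not list it as an expected occurrence. The protocol lists no death as expected, so on that test every death is unexpected and falls within the definition. An expected death would not be an SAE at all and would trigger no step, but the case does not arise on the present text.

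**3. Which steps make up the SAE route?**

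- (a) the form to the Chief Investigator, within 24 hours;
- (b) the local investigator's report to the sponsor and to the local ethics committee and/or R&D office, with no stated deadline;
- (c) the ethics report, within 15 days, if the event is related and unexpected.

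**4. How far does the exemption reach?** Two readings are open.

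- *Broad:* the exemption says these events need no reporting as SAEs, so it covers (a), (b) and (c). This is the natural reading.
- *Narrow:* the exemption directly follows the sentence on the form, and the later sentences refer to all SAEs and any SAEs without repeating it, so it covers (a) only.

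| Unexpected death | Steps that apply | Lost, broad | Lost, narrow | Stated deadlines lost, broad | Stated deadlines lost, narrow |
|---|---|---|---|---|---|
| Related | a + b + c = 3 | 3 | 1 | 2 of 2 | 1 of 2 |
| Unrelated | a + b = 2 | 2 | 1 | 1 of 1 | 1 of 1 |

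**5. Can the loss be nil?** Yes. A fatal event that was first life-threatening, or that required hospitalisation, also meets a criterion the exemption does not name. It may remain reportable on that ground. The text does not say whether that ground survives or whether the exemption overrides it.

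**6. What remains in every case?** Three provisions: all adverse events are reported; all are recorded and reviewed; and those judged significant lead to a halt and notification. The documents state no deadline for any of them. The first sends the reader back to the procedures that contain the exemption. The halt and notification depend on the researchers' assessment.

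**The case against.** The strongest reply concerns weight. A death that the researchers judged not significant is hard to imagine, so the halt and notification under the Withdrawal Criteria would almost certainly operate, and the standard procedure mentioned there may set its own deadline. The word relapse in a healthy-volunteer study suggests template wording left uncorrected rather than a deliberate rule. On this view what remains is doubt about a form and a deadline, for an event that is very unlikely. This stands as a limit on the consequence. It does not remove the conflict, and the general provisions supply neither a form nor a stated time limit.

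The step count can also be challenged, on three grounds:

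- Most fatal events would put the participant at risk of death at the time, and so meet the life-threatening criterion. On that reading the usual loss is nil. The point is fair, but the text does not settle it.
- The steps are not fully independent. The 15-day period runs from the Chief Investigator's awareness, and the 24-hour form is the SAE route to that awareness. Even on the narrow reading, losing the form could delay the start of the 15 days.
- The Regulatory Issues section has all data collected at one facility but also refers to participating NHS trusts, so it is not certain that the local report is a separate step.

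The counts are therefore best read as a range that shows how unsettled the text is.

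**Conclusion.** The contradiction holds as written. For an unexpected death, the definition brings the event into SAE reporting and the exemption takes it out. Between one and three steps are lost, depending on the reading and on relatedness, and possibly none if another criterion is accepted as an independent ground. The 24-hour deadline is in doubt on both readings. The 15-day deadline is directly removed only on the broad reading and only for a related death.

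These counts assume that the three steps are distinct and that no unseen procedure overrides the text. The conclusion is uncertainty over whether the time-limited SAE route applies to a death. It does not mean that all notification is lost. No efficacy analysis is touched. The case for correcting it rests on the seriousness of the event and the very small cost of the change, given the low probability of a death.

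**What to change.** Delete death from the list of exempted events, so that the exemption agrees with the definition and deaths follow the SAE route already described. Relapse can go in the same edit: it is not part of the contradiction but has no evident meaning in this population. Keep the exemption for elective admissions, the related-and-unexpected test for the 15-day report, and the Withdrawal Criteria provisions.

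While the section is open, confirm that the working protocol names the ethics committee printed here as xxxx. This may be a placeholder or a redaction and is not counted as an error.

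The cost is one wording change, approved by the sponsor and then sent to ethics as the Regulatory Issues section requires. That section describes ethical approval as pending, so if this is still so the change may be possible as a correction before approval. Visits, procedures and analysis are unaffected.

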6. REGULATORY ISSUES

ETHICS APPROVAL

This study is awaiting ethical approval from the Wales REC 6 Ethics Committee. The study will be conducted in accordance with the recommendations for physicians involved in research on human subjects adopted by the 18th World Medical Assembly, Helsinki 1964 and later revisions. Amendments to the protocol should be approved by the sponsor before being sent to ethics.

CONSENT

Consent to enter the study must be sought from each participant only after a full explanation has been given, an information leaflet offered, and time allowed for consideration. Signed participant consent should be obtained. The right of the participant to refuse to participate without giving reasons must be respected. After the participant has entered the study the clinician remains free to

give alternative treatment to that specified in the protocol at any stage if he/she feels it is in the participant's best interest, but the reasons for doing so should be recorded. In such cases, the participants remain within the study for the purposes of follow-up and data analyses. All participants are free to withdraw at any time from the study without giving reasons and without prejudicing further treatment.

CONFIDENTIALITY

The Chief Investigator will preserve the confidentiality of participants in the study and is registered under the Data Protection Act.

DATA AND SAMPLE COLLECTION AND ANALYSIS

All data and samples will be collected at the NIHR/Wellcome Trust Imperial Clinical Research Facility at Hammersmith Hospital. All data and samples will be stored and analysed at the laboratories of the Department of Investigative Medicine, Hammersmith Hospital. They data and samples will be available only to the study researchers. All analysis will be carried out on anonymised samples. The code linking samples to the donor will only be broken once all analysis has been conducted.

INDEMNITY

Imperial College holds negligent harm and non-negligent harm insurance policies, which apply to this study.

SPONSOR

Imperial College London will act as the main sponsor for this study. Delegated responsibilities will be assigned to the NHS trusts taking part in this study.

REIMBURSMENT

Participants will be reimbursed for their time. £75will be awarded for completion of Study 1 (£25 for completing Visits 2 –4). £100 will be awarded for completion of Study 2 (£25 for completing Visits 2 - 5). £75will be awarded for completion of Study 3 (£25 for completing Visits 2 –4)

AUDITS AND INSPECTIONS

The study may be subject to inspection and audit by Imperial College London under their remit as sponsor and other regulatory bodies to ensure adherence to GCP and the NHS Research Governance Framework for Health and Social Care (2nd edition).

